## 7.7. Study Weeks 52 Through 60 (Follow-up Assessments)

All subjects, including those who prematurely discontinue treatment or complete treatment per protocol will enter a 12-week follow-up period. Subjects will remain on ETV during the follow-up period. The following assessments are performed every 4 weeks unless otherwise indicated. A visit window of  $\pm 5$  days is applied from Weeks 52 through 60.

- Measure body weight (Week 60 only)
- Vital signs (temperature, heart rate, respiration rate and blood pressure)
- Complete physical examination (excluding breast and genitalia, unless indicated; Week 60 only)
- Symptom-directed physical examination (not at Week 60)
- 12-lead ECG (Week 60 only)
- Review concomitant medications
- Review AEs
- Laboratory analyses (additional details are provided in the Laboratory Manual):
  - Safety labs: chemistry, hematology, coagulation, urinalysis, urine pregnancy test ([Appendix 2](#))
  - Virology: HBV DNA, HBV pgRNA, HBsAg, HBeAg, HBcAg, HBsAb and HBeAb (Week 60 only), sample for HBV sequencing and HBV nucleic acids ([Appendix 2](#))
- Review dosing diary
- Assess drug accountability (final drug accountability performed at Week 60)
- Study drug dispensation (final study drug dispensation performed at Week 56)
- Study drug administration (ETV)

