## 8.1. Documenting Adverse Events

Adverse events will be monitored throughout the entire study. Investigators will ask the subject at each visit if they have experienced any untoward effects since the last study visit. All AEs (for all randomized subjects and excluding screen failures) will be entered in the electronic case report form (eCRF) provided: a description of the event, severity, time of occurrence, duration, any action (eg, treatment and follow-up tests), and the outcome should be provided along with the Investigator's assessment of the relationship to the study treatment.

Adverse events will be recorded from the date informed consent is signed through the end of study (completion of follow-up period or if the subject is lost to follow-up).

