 Final study drug dispensation of Peg-IFN $\alpha$  will occur at Week 20, 731 at Week 44, and ETV at Week 56. Final study drug accountability of Peg-IFN $\alpha$  is performed at Week 24, 731 at Week 48, and ETV at Week 60.

 731 and ETV administration are in-clinic at the study visits and self-administered once daily at home on all other days. Day 1 Peg-IFN $\alpha$  administration is in-clinic for injection training purposes; subsequently, subjects will administer Peg-IFN $\alpha$  once weekly at home.

 Dosing with Peg-IFN $\alpha$  (if applicable) will stop at Week 24. Dosing with 731 (if applicable) will stop at Week 48. Dosing with ETV will continue until Week 60.

 If the subject inadvertently administers study drug prior to collection, a PK sample should still be drawn. Refer to [Section 7.11](#).

 Predose PK samples for 731, ETV, and Peg-IFN $\alpha$  on Day 1 and Weeks 4 and 24. Postdose PK samples for 731, ETV, and Peg-IFN $\alpha$  may be collected from 2 to 4 hours postdose on Day 1, and between 30 min and 2 hours after in-clinic study drug administration at Weeks 2, 8, 12, and 24. Postdose samples at Weeks 16 and 20 may be collected between 4 and 6 hours after in-clinic study drug administration. Predose samples for ETV may be collected at Week 44.

 HBcAb IgM testing may be performed for some subjects at Screening, see Inclusion Criterion #5, [Section 5.2](#).

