## 1. INTRODUCTION

Study ABI-H0731-203 is a randomized Phase 2a, multicenter, open-label study evaluating vebicorvir (VBR; formerly ABI-H0731) -containing regimens in subjects with chronic hepatitis B virus (HBV) infection (cHBV). The target population is male or female subjects, 18 to 65 years of age, inclusive, treatment naïve with hepatitis B virus “e” antigen (HBeAg) positive cHBV and no evidence of cirrhosis or end-stage liver disease.

This statistical analysis plan (SAP) describes the statistical analysis methods and data presentations to be used in tables, figures, and listings (TFLs) in the clinical study report (CSR) for Study ABI-H0731-203. This SAP is based on the study protocol amendment 3, dated 29 July 2021 and the electronic case report form (eCRF). In July 2022, Assembly made the decision to terminate this study and discontinue the development of VBR after review of interim data suggested that none of the study drug regimens were likely to lead to functional cure. Subsequently, participants in Study ABI-H0731-203 ended study treatment and entered in follow-up period with entecavir (ETV) for 12 weeks. . Therefore, only key safety and efficacy endpoints will be performed for this study. The SAP will be finalized before database lock. Any changes made after the finalization of the SAP will be documented in the Synoptic CSR.

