### **3.6. Analysis Visit Windows**

#### **3.6.1. Definition of Study Drug**

In this study, study drugs are defined as VBR, ETV, and Peg-IFN $\alpha$ .

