#### **3.6.2. Definition of Study Phase**

The following phases will be defined: Randomized Treatment Phase and Overall Treatment Phase are on treatment; and the Follow-up Phase is off treatment.

- Randomized Treatment Phase: from first dose date through Week 24 visit (or premature termination visit if before Week 24)
- Overall Treatment Phase: from first dose date through Week 48 visit (or premature termination visit if before Week 48)
- Follow-up Phase: after Week 48 visit (or premature termination visit) through end of study

End of study will be when the subject completes the last visit of the follow-up period or is considered “lost to follow-up,” whichever is later.

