#### **3.6.3. Definition of Study Day**

The first dose date of VBR when administered in combination with ETV with or without Peg-IFN $\alpha$  will be calculated where applicable. Study Day 1 is defined as the first dose date of study drug, which is the earliest/minimum of the first dose dates of VBR, ETV, and Peg-IFN $\alpha$  in a treatment group. If the first dose date is missing, the date of randomization will be used.

The last dose date of VBR, ETV, and of Peg-IFN $\alpha$  will be calculated where applicable. For the Randomized Treatment Phase, the last dose date of study drug VBR will be the Week 24 visit date or the end date on study drug administration CRF if a subject discontinued study drug prior to Week 24 visit. For study drug ETV, the last dose date will be obtained from End of Treatment-ETV eCRF. For study drug Peg-IFN $\alpha$ , the last dose date will be obtained from End of Treatment-Peg-IFN $\alpha$  eCRF. For the Overall Treatment Phase, the last dose date for each drug will be the end date on the respective End of Treatment eCRF pages. The last dose date of study drug will be defined as the latest/maximum of the last dose dates of VBR, ETV, and Peg-IFN $\alpha$  in a treatment group.

For the on-treatment phases, Study Day will be calculated from Study Day 1 and derived as follows:

- For days prior to the first dose: Assessment Date – Study Day 1
- For postdose study days: Assessment Date – Study Day 1 + 1

For the Follow-up Phase, the follow-up Study Day 1 is defined as the day after Week 48 visit or Premature Termination visit. The follow-up study day will be derived as Assessment Date – follow-up Study Day 1 +1.

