#### **7.1.6. Summaries of Adverse Events and Deaths**

Treatment-emergent AEs will be summarized based on the Safety Analysis Set for the Randomized Treatment Phase (up to the last dose at Week 24) and the Overall Treatment Phase (up to the last dose of any study drug plus 28 days).

A brief, high-level summary of the number and percentage of subjects who experienced at least 1 TEAE in the categories described below will be provided by treatment group. The brief summary will also include treatment-related TEAEs, and treatment-related TE SAEs. In addition, a table for each category showing the number and percentage of subjects will be provided by PT and treatment group in descending order of total frequency:

- TEAEs
- TEAEs by severity grade
- TEAEs related to VBR
- TEAEs related to ETV
- TEAEs related to Peg-IFN $\alpha$
- TE SAEs
- TE SAEs related to VBR
- TE SAEs related to ETV
- TE SAEs related to Peg-IFN $\alpha$
- TEAEs leading to VBR discontinuation
- TEAEs leading to ETV discontinuation
- TEAEs leading to Peg-IFN $\alpha$  discontinuation

- TEAEs leading to study discontinuation
- COVID-19 specific TEAEs
- COVID-19 specific TE SAEs

Multiple events will be counted only once per subject in each summary. For summary by severity grade, the most severe grade will be used for those AEs that occurred more than once in an individual subject during the study.

For the Follow-up Phase, a summary table will also be provided for all the AEs that occurred after the last dose of any study drug + 28 days through the end of study by the above category and by PT.

A data listing containing all AEs will be provided.

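### As written, the Follow-up adverse event table has no eligible days for subjects who stay on entecavir, and their entecavir-only time is counted in the Overall Treatment Phase

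*Combined protocol and SAP*

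**What the plan says.** Several SAP and protocol provisions combine to set the safety windows.

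- **Study drug.** SAP 3.6.1: "In this study, study drugs are defined as VBR, ETV" and Peg-IFNα.
- **Last dose.** SAP 3.6.3: "The last dose date of study drug will be defined as the latest/maximum of the last dose dates of VBR, ETV" and Peg-IFNα. For the Overall Treatment Phase each date comes from that drug's End of Treatment eCRF page. No separate cut at Week 48 is stated for ETV.
- **AE tables.** SAP 7.1.6 runs the Overall Treatment Phase tables to the last dose of any study drug plus 28 days. The Follow-up table takes "all the AEs that occurred after the last dose of any study drug + 28 days through the end of study".
- **Laboratory tables.** SAP 7.2.1.1 uses the same cut-off for treatment-emergent laboratory abnormalities in the Overall Treatment Phase, and 7.2.1.2 bases its denominators on it.
- **ETV in follow-up.** Protocol 7.7: "Subjects will remain on ETV during the follow-up period". Protocol Appendix 1, footnote 19: "Dosing with ETV will continue until Week 60". SAP 1 reports that after the July 2022 termination participants "ended study treatment and entered in follow-up period with entecavir (ETV) for 12 weeks".
- **AE recording.** Protocol 8.1 records AEs "through the end of study (completion of follow-up period or if the subject is lost to follow-up").
- **Phase definition.** SAP 3.6.2 defines the Overall Treatment Phase as "from first dose date through Week 48 visit (or premature termination visit if before Week 48"). It starts the Follow-up Phase right after that visit and labels it off treatment.
- **Size of the phase.** SAP 4.2.1 expects 48 weeks of exposure in the Overall Treatment Phase, and 4.2.2.1 expects 336 ETV tablets.

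**The concern.** The 28-day tail is attached to a drug that nearly everyone takes until the day observation ends, so the Follow-up AE window opens after AE recording has closed. The planned Follow-up AE summary can then hold only atypical subjects. These are people who stopped ETV more than 28 days before the end of study (ETV is at the investigator's discretion after early discontinuation, protocol 7.10.1), or people seen beyond the last visit for an unresolved ALT elevation (protocol 9.4).

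Safety and tolerability of VBR is the primary objective. AEs that begin after VBR and Peg-IFNα have stopped would be tabulated with on-regimen events, while a nearly empty Follow-up table could be taken as evidence that nothing happened after VBR was withdrawn. Exposure and AE tables bearing the same phase label would also describe different periods.

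**Working it through.** **Inputs (nominal days, 7 per week).** Week 48 = 336 and Week 60 = 420 (visit schedule, protocol Appendix 1). The tail is 28 days (SAP 7.1.6). Last ETV dose for a completer: day 420 (Appendix 1, footnote 19). AE recording ends at completion of follow-up, day 420 (protocol 8.1).

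**Plan's own figure.** Follow-up Day 1 is the day after the Week 48 visit, day 337 (SAP 3.6.3). Week 60 is then follow-up day 420 − 337 + 1 = 84, matching FU-Week 12 = day 84 in SAP Table 3-6. So SAP 3.6.2 intends 84 days of follow-up.

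**Eligible days under SAP 7.1.6.** Eligible days = max(0, end of study − (last dose of any study drug + 28)).

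- Completer on ETV to Week 60: 420 + 28 = 448; max(0, 420 − 448) = 0. The result is still 0 if the Week 60 visit falls on day 415 or 425 (the ±5-day window), or if the last ETV dose is the day before the visit.
- Subject stopped on day T, then 12 weeks (84 days) of ETV: the cut-off is T + 84 + 28 = T + 112 and the end of study is T + 84, so 0 for any T.

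**Who can contribute time.** With end of study on day 420, at least one eligible day needs a last ETV dose no later than 420 − 28 − 1 = 391, just before Week 56 (day 392).

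| Last ETV dose | Eligible Follow-up AE days |
|---|---|
| Week 48 | 56 |
| Week 52 | 28 |
| Week 54 | 14 |
| Week 56 | 0 |
| Week 60 | 0 |

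**Where the time goes.** ETV-only days for a completer: 420 − 336 = 84, all inside the Overall Treatment Phase AE window. That is 84/420 = 20% of the observed window, which is 420/336 = 1.25 times the length SAP 4.2.1 gives the phase.

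**Early termination.** With d the last VBR or Peg-IFNα day, the ETV-only share is 84/(d + 84). The documents do not give individual stop dates, so these values are illustrative.

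| Assumed stop | d | Share |
|---|---|---|
| Week 12 | 84 | 50% |
| Week 24 | 168 | 33% |
| Week 36 | 252 | 25% |
| Week 47 | 329 | 20% |

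**With one boundary, completer.**

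- Last VBR or Peg-IFNα dose + 28: 336 + 28 = 364. Follow-up is days 365 to 420, or 56 days, and ETV-only time in the Overall tables is 28/364 = 7.7%.
- SAP 3.6.2 visit boundary, no tail: Follow-up is 420 − 336 = 84 days, with no ETV-only time in the Overall tables.

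**The case against.** The best counter-argument is that the SAP may not mean follow-up ETV to count. The sentence on End of Treatment pages is scoped to the Overall Treatment Phase, which SAP 3.6.2 ends at Week 48. SAP 1 says participants had ended study treatment when they entered ETV follow-up, and 3.6.2 calls that phase off treatment. The ETV eCRF page is not in the documents, so the date it holds is unverified. On that reading the last dose is about Week 48 and the Follow-up AE table covers about 56 days.

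This does not remove the problem. No sentence exempts follow-up ETV from the study drugs, and Appendix 1 (footnotes 17 and 19) places the last ETV dosing and accountability at Week 60. Even with a Week 48 date the AE table would open on day 365, 28 days after SAP 3.6.2 opens the phase on day 337, so the two sections would still disagree.

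Other points do stand and limit the weight of the finding:

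- The Randomized Treatment Phase tables stop at the Week 24 dose, so they hold no follow-up time for subjects who complete Week 24. That is the period when the randomized regimens differ.
- Planned ETV-only follow-up is the same in all groups, so the rule favours none by design.
- Related events and discontinuations are tabulated separately by drug, and every AE is listed. Events are misplaced, not lost.
- Vital signs and ECG are summarised by visit and are unaffected. Follow-up laboratory abnormalities have their own summary. If that summary uses the SAP 3.6.2 phase, those values would be counted in both periods.
- A share of time is not a share of AEs; the documents give no event rates.
- Counting AEs during ETV dosing as treatment-emergent is reasonable. The fault lies in using that flag as the phase boundary.

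**Conclusion.** The concern holds. Read literally, SAP 3.6.1, 3.6.3 and 7.1.6 give 0 eligible Follow-up AE days to any subject who stays on ETV to the end of follow-up, and place 84 ETV-only days in the Overall Treatment Phase tables. This conflicts with the phase definition in SAP 3.6.2 and with the 48 weeks and 336 ETV tablets in 4.2.1 and 4.2.2.1. The 0 assumes that the End of Treatment-ETV page carries the final ETV date and that AE recording stops at completion of follow-up. The inconsistency between 3.6.2 and 7.1.6 does not depend on the first of these.

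It should be fixed because it affects summary tables for the primary objective. It is not more serious than that: the analysis is descriptive, the report is a synoptic one for a terminated study, and the listings allow the events to be reassigned.

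**What to change.** State one phase boundary in SAP 3.6.2 and 3.6.3 and use it in 7.1.6, 7.2.1.1 and 7.2.1.2. Two choices work:

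1. End the Overall Treatment Phase AE and laboratory tables 28 days after the later of the last VBR and Peg-IFNα doses, and start the Follow-up (ETV-only) tables the next day.
2. Keep the existing visit boundary of SAP 3.6.2 with no tail, accepting that AEs in the first 28 days after VBR stops then appear under Follow-up.

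Under either choice, let SAP 7.1.5.1 keep flagging AEs during ETV dosing as treatment-emergent, so that ETV-related events remain visible, but assign each AE to a phase by onset date. Add to 7.1.5.2 a rule that assigns incomplete onset dates to a phase. A separate Week 24 to 48 table for Group 3, which first receives VBR at Week 24, is optional.

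The cost is revised wording in up to seven SAP sections, one phase flag in the AE and laboratory datasets, and re-run tables. No new data are needed. Under SAP 1, a change made after the SAP is final is documented in the Synoptic CSR.

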## **7.2.           Laboratory Evaluations**

Laboratory data collected during the study will be analyzed and summarized using both quantitative and qualitative methods based on the Safety Analysis Set. The lab values that are below LLOQ or above the upper LOQ will be listed as such, and the closest imputed value will be used for the purpose of calculating summary statistics as specified in [Section 3.4](#).

### **7.2.1.       Graded Laboratory Values**

The criteria specified in the study protocol will be used to grade laboratory results as normal (no grade), mild (Grade 1), moderate (Grade 2), severe (Grade 3) or potentially life threatening (Grade 4). See Appendix 3 of the protocol for detailed DAIDS grading criteria on the relevant laboratory tests. For laboratory tests with criteria for both increased and decreased levels, analyses for each direction (i.e., increased, decreased) will be presented separately.

#### **7.2.1.1.      Treatment-Emergent Laboratory Abnormalities**

Treatment-emergent laboratory abnormalities are defined as values that increase at least 1 toxicity grade from Baseline at any postbaseline time point, up to and including the date of last dose of any study drug plus 28 days for the Overall Treatment Phase. For the Randomized Treatment Phase, the treatment-emergent laboratory abnormalities will be summarized up to the last dose at Week 24.

If the relevant baseline laboratory value is missing, any abnormality of at least Grade 1 observed within the time frame specified above will be considered treatment emergent.

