10. History of malignancy other than HCC unless the subject's malignancy has been in complete remission off chemotherapy and without additional medical or surgical interventions during the 3 years before Screening

11. History or presence at Screening of electrocardiogram (ECG) abnormalities deemed clinically significant, in the opinion of the Investigator
12. History of hypersensitivity or idiosyncratic reaction to any components or excipients of the investigational drug
13. History of any significant food or drug-related allergic reactions such as, anaphylaxis or Stevens-Johnson syndrome
14. The following exclusionary laboratory results at Screening:
  - Hemoglobin <12g/dL for males or <11g/dL for females
  - Platelet count <100,000/mm^3
  - White blood cell count <2,500/mm^3
  - Absolute neutrophil count <1,500/mm^3
  - Albumin <lower limit of normal
  - History of thyroid disease poorly controlled on prescribed medications, with thyroid-stimulating hormone (TSH), free triiodothyronine or free thyroxine (T4) outside the normal limits
  - Total bilirubin >1.2 × ULN unless known Gilbert's syndrome; subjects with Gilbert's syndrome are eligible for study participation if the direct bilirubin is within the normal range
  - Direct bilirubin >1.2 × ULN
  - ALT ≤1 × ULN or ≥10 × ULN
  - Serum alpha fetoprotein (AFP) ≥100 ng/mL. If AFP at Screening is > ULN but <100 ng/mL, the subject is eligible if hepatic imaging prior to initiation of study drug reveals no lesions indicative of possible HCC
  - International Normalized Ratio (INR) >1.5 × ULN (unless on a stable anticoagulant regimen)
  - Glomerular filtration rate <60 mL/min/1.73 m^2 by Chronic Kidney Disease Epidemiology Collaboration equation ([Levey et al 2009](#))
  - Serum creatinine >1.5 × ULN
  - Any other laboratory abnormality deemed clinically significant by the Sponsor or the Investigator
15. Subjects receiving prohibited concomitant medications or medications that should be avoided (as outlined in [Section 6.6](#) and [Appendix 5](#)) within 7 days or 5 half-lives (if known), whichever is longer, prior to administration of the first dose of study drug (Day 1) and for the duration of the study period. Please refer to Exclusion Criterion #1 for criteria regarding liver protecting and/or ALT lowering agents

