## **9.4. Management of ALT Elevations**

All subjects participating in the study will be closely monitored for ALT elevations and/or signs of potential decline in hepatic function. Subjects experiencing ALT elevations  $\geq 2 \times$  Baseline or on-treatment nadir and  $> 2 \times$  ULN during study treatment or during post-treatment follow-up should be closely monitored with regular Unscheduled Visits every 1 to 2 weeks at the discretion of the Investigator. At these visits, the following laboratory tests will be performed: ALT, aspartate aminotransferase (AST), total bilirubin (if total bilirubin is elevated, reflex to direct bilirubin), serum albumin, INR and creatine kinase. The Investigator will determine if other Unscheduled Visit

assessments ([Section 7.8](#)) should be performed. Additionally, the following guidance is provided for management of subjects with ALT elevations:

- ALT elevation without declining hepatic function
  - All subjects with an ALT elevation on treatment, defined as ALT  $>2 \times$  Baseline or on-treatment nadir and  $\geq 10 \times$  ULN, should have the ALT findings confirmed within 3 days of receipt of the original results. All subjects should return for an Unscheduled Visit and complete all Unscheduled Visit procedures ([Section 7.8](#)).
  - If the ALT elevation is confirmed, then an additional Unscheduled Visit will be performed to further evaluate the subject. At this visit, the following tests will be performed: ALT, AST, total bilirubin (if total bilirubin is elevated, reflex to direct bilirubin), serum albumin, INR, creatine kinase, HBV DNA, quantitative HBV serologies (HBeAg [reflex qualitative HBeAg if quantitative HBeAg is less than the lower limit of quantification (LLOQ)] and HBsAg [reflex qualitative HBsAg if quantitative HBsAg is  $<$ LLOQ]), HAV IgM, HCV RNA, HDV RNA, and HEV IgM. The Investigator will determine if other assessments specified in [Section 7.8](#) should be performed.
    - If an intercurrent illness is determined to be causal, subjects with an ALT elevation without declining hepatic function and without contraindications may continue assigned treatment (ie, 731, ETV and Peg-IFN $\alpha$  as applicable) and the intercurrent illness should be treated as deemed medically appropriate by the Investigator.

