Urinary Tract Obstruction	NA	Signs or symptoms of urinary tract obstruction without hydronephrosis or renal dysfunction	Signs or symptoms of urinary tract obstruction with hydronephrosis or renal dysfunction	Obstruction causing life-threatening consequences

Abbreviation: NA = not applicable.

Laboratory Values k: Chemistries				
Parameter	Grade 1 Mild	Grade 2 Moderate	Grade 3 Severe	Grade 4 Potentially Life-threatening
Acidosis	NA	pH $\geq$ 7.3 to <LLN	pH <7.3 without life-threatening consequences	pH <7.3 with life-threatening consequences
Albumin, Low (g/dL; g/L)	3.0 to <LLN 30 to <LLN	$\geq$ 2.0 to <3.0 $\geq$ 20 to <30	<2.0 <20	NA
Alkaline Phosphatase, High	1.25 to <2.5 $\times$ ULN	2.5 to <5.0 $\times$ ULN	5.0 to <10.0 $\times$ ULN	$\geq$ 10.0 $\times$ ULN
Alkalosis	NA	pH >ULN to $\leq$ 7.5	pH >7.5 without life-threatening consequences	pH >7.5 with life-threatening consequences
ALT or SGPT, High Report only one	1.25 to <2.5 $\times$ ULN	2.5 to <5.0 $\times$ ULN	5.0 to <10.0 $\times$ ULN	$\geq$ 10.0 $\times$ ULN
Amylase (Pancreatic) or Amylase (Total), High Report only one	1.1 to <1.5 $\times$ ULN	1.5 to <3.0 $\times$ ULN	3.0 to <5.0 $\times$ ULN	$\geq$ 5.0 $\times$ ULN
AST or SGOT, High Report only one	1.25 to <2.5 $\times$ ULN	2.5 to <5.0 $\times$ ULN	5.0 to <10.0 $\times$ ULN	$\geq$ 10.0 $\times$ ULN
Bicarbonate, Low (mEq/L; mmol/L)	16.0 to <LLN 16.0 to <LLN	11.0 to <16.0 11.0 to <16.0	8.0 to <11.0 8.0 to <11.0	<8.0 <8.0
Bilirubin Direct Bilirubin, High	NA	NA	>ULN with other signs and symptoms of hepatotoxicity	>ULN with life-threatening consequences (eg, signs and symptoms of liver failure)
Total Bilirubin, High	1.1 to <1.6 $\times$ ULN	1.6 to <2.6 $\times$ ULN	2.6 to <5.0 $\times$ ULN	$\geq$ 5.0 $\times$ ULN
Calcium, High (mg/dL; mmol/L)	10.6 to <11.5 2.65 to <2.88	11.5 to <12.5 2.88 to <3.13	12.5 to <13.5 3.13 to <3.38	$\geq$ 13.5 $\geq$ 3.38
Calcium (Ionized), High (mg/dL; mmol/L)	>ULN to <6.0 >ULN to <1.5	6.0 to <6.4 1.5 to <1.6	6.4 to <7.2 1.6 to <1.8	$\geq$ 7.2 $\geq$ 1.8
Calcium, Low (mg/dL; mmol/L)	7.8 to <8.4 1.95 to <2.10	7.0 to <7.8 1.75 to <1.95	6.1 to <7.0 1.53 to <1.75	<6.1 <1.53
Calcium (Ionized), Low (mg/dL; mmol/L)	<LLN to 4.0 <LLN to 1.0	3.6 to <4.0 0.9 to <1.0	3.2 to <3.6 0.8 to <0.9	<3.2 <0.8

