### 3.6.4. Analysis Visit Windows

Subject visits might not occur on protocol-specified days. Therefore, for the purpose of analysis, observations will be assigned to analysis windows. In general, the baseline value will be the last nonmissing value on or prior to the first dose date of study drug. The on-treatment phases include Randomized Treatment Phase and Overall Treatment Phase. For the Randomized Treatment Phase, the data will be summarized up to the Week 24 visit or premature termination visit. For the Overall Treatment Phase, the data will be summarized up to the Week 48 visit or premature termination visit. For the Follow-up Phase, the data will be summarized from follow-up Study Day 1 through the end of study, where Follow-Up Baseline data is from Week 48 visit or premature termination visit.

The analysis windows for the on-treatment HBV DNA and HBV pgRNA assessments are provided in Table 3-1.

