### 7.2.1.2. Summaries of Laboratory Abnormalities

A summary (number and percentage of subjects) for treatment-emergent laboratory abnormalities will be provided by lab test and treatment group; subjects will be categorized according to the most severe postbaseline abnormality grade for a given lab test.

For all summaries of laboratory abnormalities, the denominator is the number of subjects with nonmissing postbaseline values up to 28 days after last dose date for the Overall Treatment Phase and up to Week 24 dose date for the Randomized Treatment Phase.

The maximum postbaseline grade observed up to 28 days after last dose date or the Week 24 dose date will be tabulated for each laboratory test, and percentages will be based on the number of subjects with a postbaseline evaluation of the specific laboratory test. The laboratory abnormalities during the Follow-up Phase will also be summarized.

A by-subject listing of graded laboratory abnormalities will be provided by subject number and visit in chronological order. This listing will include all test results that were collected throughout the study for the lab test of interest, with all applicable severity grades displayed.

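### Treatment-emergent ALT grades are judged only against Baseline, so a flare after ALT has normalised counts only if it exceeds the Baseline grade, and the SAP's other ALT summaries only partly fill that gap

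*Combined protocol and SAP*

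**What the plan says.** **Graded rule.** SAP 7.2.1.1 counts as treatment-emergent only "values that increase at least 1 toxicity grade from Baseline at any postbaseline time point". The one exception is a missing baseline: "If the relevant baseline laboratory value is missing, any abnormality of at least Grade 1" then counts. Under SAP 3.6.4 "the baseline value will be the last nonmissing value on or prior to the first dose date of study drug", which will normally be the Day 1 predose sample.

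**Entry ALT.** Protocol 5.3, criterion 14, excludes "ALT ≤1 × ULN or ≥10 × ULN" at Screening. Protocol Appendix 3 grades ALT in multiples of ULN: Grade 1 from 1.25 to <2.5, Grade 2 from 2.5 to <5, Grade 3 from 5 to <10, Grade 4 from 10.

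**The protocol's comparator.** Protocol 9.4 judges ALT elevation against "Baseline or on-treatment nadir", during treatment and post-treatment follow-up. Its close-monitoring threshold is at least a doubling and >2 × ULN.

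**Other planned outputs.**
- SAP 7.2.1.2: "The maximum postbaseline grade observed up to 28 days after last dose date or the Week 24 dose date will be tabulated" for each test, with a by-subject listing of graded results. It adds that "The laboratory abnormalities during the Follow-up Phase will also be summarized", without naming a comparator.
- SAP 7.2.2.2: an ALT component of ≥2 × Baseline or nadir and >2 × ULN, summarised by treatment group. Individual tests are counted once, on the most severe postbaseline value. No split by phase is stated.
- Protocol 8.5: an abnormality that the Investigator considers clinically significant is reported as an AE.

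**The concern.** Abnormal laboratory results are part of the primary endpoint (Protocol 3.2.1), and the graded tables are the main planned summary of them by phase. ALT normalisation is itself a secondary objective (Protocol 3.1.2), so a fall from a raised Baseline is a course that the trial sets out to observe. Once ALT has fallen, a comparator fixed at the raised Baseline no longer describes the subject's state. A large rise from normal can then score as no change in grade. The loss increases with Baseline grade, so the table is least sensitive in the subjects who start with the highest ALT. Protocol 9.4 already allows for this by adding the nadir as a comparator. The graded table does not.

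**Working it through.** There is no planned figure to reproduce: the question concerns a definition, and the sample size has no statistical basis (Protocol 10.1). The check applies the Appendix 3 bands to the SAP rule.

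**1. Lowest later value that counts.** The rule is: treatment-emergent if postbaseline grade ≥ Baseline grade + 1.

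| Baseline grade | Baseline ALT (× ULN) | Lowest value that counts (× ULN) | Flare grades not counted |
|---|---|---|---|
| 0 | <1.25 | 1.25 | none |
| 1 | 1.25 to <2.5 | 2.5 | 1 |
| 2 | 2.5 to <5 | 5 | 1–2 |
| 3 | 5 to <10 | 10 | 1–3 |

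**2. Examples.** Assume a normalised nadir of 0.8 × ULN (illustrative; not in the documents).
- Baseline 6, nadir 0.8, flare 9.9: Grade 3 − Grade 3 = 0, so not treatment-emergent, although 9.9 / 0.8 = 12.4 times nadir.
- Baseline 3, nadir 0.8, flare 4.9: Grade 2 − Grade 2 = 0, so not treatment-emergent, although 4.9 / 0.8 = 6.1 times nadir.
- Both flares meet ≥2 × nadir and >2 × ULN. The first does so for any nadir up to 9.9 / 2 = 4.95 × ULN, and the second up to 4.9 / 2 = 2.45, so the result does not depend on 0.8.

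**3. Does the maximum-grade table show the flare?** Take two courses, in × ULN with Baseline first.
- A: 6.0, 5.9, 0.8, 5.0 (late flare).
- B: 6.0, 5.9, 0.8, 0.8 (no flare).

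The maximum postbaseline value is 5.9 in both, Grade 3. The table cannot tell A from B.

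**4. Does SAP 7.2.2.2 show it?** The most severe postbaseline value in course A is 5.9.
- Reading nadir as the lowest earlier value: 5.9 / 6.0 = 0.98, below 2, and no lower value precedes it. The criterion is not met and the flare is missed.
- Reading nadir as the lowest value at any time: 5.9 / 0.8 = 7.4, so the criterion is met. It is then met equally in course B, which has no flare.
- Evaluated visit by visit against the lowest earlier value: 5.0 / 0.8 = 6.25 and 5.0 > 2, so A is counted. In B, 5.9 fails as above and 0.8 is not above 2, so B is not counted.

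Where no higher carry-over value precedes the flare, as in step 2 if ALT falls directly from 6 to 0.8, the most severe value is the flare itself and SAP 7.2.2.2 does count it.

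**5. Would a one-grade rise from nadir be better?** No. A move from 2.4 to 2.5 × ULN (2.5 / 2.4 = 1.04, about 4%) changes the grade from 1 to 2 and would be flagged. The doubling threshold already in SAP 7.2.2.2 avoids this.

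**The case against.** The strongest defence is that worsening from the pre-treatment value is a coherent meaning of treatment-emergent, and that flares have their own section. SAP 7.2.2.2 does use the nadir, by treatment group, and lists the subjects who meet a criterion. A flare to 9 × ULN also appears as Grade 3 in the maximum-grade table and in the listing. Any value meeting the ≥10 × ULN definition in Protocol 9.4 and SAP 7.2.2.1 is Grade 4, so it is treatment-emergent for every subject whose Baseline is below 10 × ULN. The trial stopped early and supports a synoptic report without formal inference. All of this stands. It reduces the point to incomplete cover, and it is a reason to leave the graded definition alone. It does not answer steps 3 and 4 of the working.

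A reader might infer more than the documents support:
- **That these flares are reported nowhere.** The outputs just listed contradict this.
- **That the ≥5 × ULN stratum is Grade 3 at Baseline.** Stratification uses the Screening value, up to 45 days before Day 1, while grading uses the last value on or before first dose.
- **That nearly all subjects enter with graded ALT.** Values >1 to <1.25 × ULN are eligible and ungraded, and no ALT distribution is given.
- **That AST has the same problem.** Criterion 14 sets no AST limit, and the nadir rule in Protocol 9.4 concerns ALT only.
- **That flares are expected when Peg-IFNα stops at Week 24 or 731 at Week 48.** The documents require monitoring but predict no timing, and entecavir continues through both changes.

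**Conclusion.** The point holds for ALT, as a gap in how flares after normalisation are summarised. Under SAP 7.2.1.1 such a flare is not treatment-emergent unless it exceeds the Baseline grade. From Baseline Grade 3, no rebound below 10 × ULN counts; from Grade 2, none below 5; from Grade 1, none below 2.5; from Grade 0, nothing is lost. SAP 7.2.2.2 covers part of this, but its value-selection rule can miss a flare that follows a higher carry-over value, and it states no phase split. The maximum-grade table cannot separate the two.

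The conclusion rests on the Appendix 3 bands, on Baseline as defined in SAP 3.6.4, and on a literal reading of the most-severe-value rule. The nadir of 0.8 × ULN is illustrative. The documents give neither a Baseline ALT distribution nor a flare rate, so the number of subjects affected cannot be computed.

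**What to change.** Keep the Baseline-based graded table as it is. In SAP 7.2.2.2:
- Evaluate the existing ALT component at every postbaseline visit: ≥2 × Baseline or ≥2 × the lowest earlier value, and >2 × ULN. Count a subject who meets it at any visit. State that nadir means the lowest value before the one being judged.
- Report the count by treatment group for the Randomized Treatment, Overall Treatment and Follow-up Phases. In follow-up, add the Follow-Up Baseline of SAP 3.6.4 as a comparator.
- Show these rows beside the Baseline-graded ALT rows.

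The change is to the analysis only. It needs no new data and does not touch the management rules in Protocol 9.4. The cost is one derived variable and a few extra rows, and reported ALT flare counts will be somewhat higher. If the SAP is already final, SAP 1 provides for recording the change in the Synoptic CSR.
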